8 TRIAL PROCEDURES

8.1 Trial randomisation

In order to avoid contamination between physicians working in the same practice randomization will happen at the level of the general practice.

General practices and community paediatric centres will be randomized in one of the 2 study arms in a 1:1 ratio using a block randomization system stratified per recruiting academic centre in order to guarantee that allocation to either usual care or the intervention arm is balanced within every region.

Stratified block randomization will be done using an electronic random numbers generator in blocks of 4 practices. Randomisation and concealment will be centralised at the KU Leuven and conducted by a staff member not involved in data collection or delivering the intervention.

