8.4 Recruitment

Given the current special circumstances under the COVID-19 pandemic, we aim to recruit practices during two stages, with stage 1 acting as a run-in period before all practices will be asked to start recruiting patients. The first stage will allow the study team to recruit a smaller number of practices in a selection of the participating academic centres to further streamline the recruitment process and remedy any unforeseeable issues that might occur after the investigator meeting and study initiation. In a second stage more practices will be recruited both at the initial academic centres as well as the other participating academic centres. We aim to keep recruitment of practices as pragmatic as possible to limit the burden on practices dealing with the aftermath of the COVID-19 pandemic.

For the recruitment of general practices, each academic centre will regionally, according to their own customs for recruitment (and what training may be part of the recruitment process), approach physicians. A website with information about the trial could help the recruitment process. The website will contain a form, which can be completed by GPs. GP's can express their interest in the study without further obligations. The study teams of the

AC can contact the GP for a thorough explanation of the study, once approval of the ethics research committees is obtained. However, the information provided at the investigator meetings will be standardised and contain short and practical training on the new guidelines.

Both solo general practices and group practices are eligible for participation in the trial. Per general practice ideally only 1 or 2 physicians will be selected for participation in the study, in order not to dilute the number of patients per physician and thus to minimize the possibility of a strong selection of patients towards the most motivated - as perceived by the physician - and for practical reasons.

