11.3.2 Primary outcome analysis

The primary endpoint will be analyzed according to the intent-to-treat (ITT) approach.

We will use a mixed-effects logistic regression analysis to account for the clustering at practice level, and other potential interaction terms, such as the child's age.

Multiple imputation will be applied to deal with missing data. Imputation will be performed for the binary outcome variable and logistic regression will be used as imputation model. Predictors for the imputation model are baseline patient characteristics and intervention.

Subgroup analysis will be performed in order to investigate how the primary outcome behaves in function of:

- age categories
- gender

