- multicentre: six academic centres for primary care will be involved in the recruitment of 122 primary care practices
- pragmatic: criteria excluding patients from participation will be limited as well as procedures that do not reflect care as usual
- cluster: randomization occurs at the level of the primary care practice while patients are the unit of analysis
- randomized: block randomization per academic centre will be performed to assign primary care practices to either the intervention or the control arm
- controlled: the intervention will be compared with usual care
- superiority: the trial is designed to show that the intervention is superior to usual care

Randomization

In order to avoid contamination between physicians working in the same practice, randomization will happen at the level of the physician's practice.

General practice clinics and community paediatric centres will be randomized in one of the two study arms in a 1:1 ratio using a block randomization system stratified per recruiting academic centre in order to guarantee that allocation to either the usual care or the intervention arm is balanced within every region.

Stratified block randomization will be done using an electronic random numbers generator in blocks of four practices. Randomization and concealment will be centralized at the KU Leuven and conducted by a staff member not involved in data collection or delivering the intervention.

Sample size calculation

The original sample size calculation in the approved protocol version 2.0 was based on previous data from the ERNIE2 trial, assuming an overall antibiotic prescribing proportion of 26.5% in those children recruited for our trial.

The overall antibiotic proportion was found to be 18% in the first 4938 patients recruited in the ARON trial.

If we were to assume a reduction of 5.3% (proportionate to our original reduction) between the usual care group and the intervention group, using a 5% significance level (alpha 0.05), an intracluster correlation coefficient (ICC) of 0.063 (based on data from the ERNIE2 trial in the exact same population), and power of 90% (beta 0.1), this would require 63 clusters of 50 patients in both arms, resulting in 6300 children.

R code:

We used the n4props-function in the R package CRTSize, using the following command: n4props(pc = 0.2065, pe = 0.1435, m = 50, ICC = 0.063, alpha = 0.05, power=0.9, AR=1, two.tailed=TRUE, digits=3).

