The primary outcome is the proportion of subjects who were prescribed antibiotic treatment (both immediate and delayed) at the index consultation as recorded by the treating physician.

Secondary endpoints:

- The duration (in days) until reaching full clinical recovery
- The proportion of subjects receiving additional testing (including, but not limited to (X-Ray, blood tests, urine tests) at index consultation (day 0) and/or during follow-up (day 1 to day 30)
- The proportion of subjects who re-consulted their physician during follow-up (day 0 to day 30)
- The proportion of subjects who were prescribed antibiotic treatment during follow-up (immediately after index consultation to day 30)

Exploratory endpoints:

- The proportion of subjects receiving additional testing (including, but not limited to (X-Ray, blood tests, urine tests) at index consultation (day 0)
- The proportion of subjects receiving additional testing (including, but not limited to (X-Ray, blood tests, urine tests) during follow-up (day 1 to day 30)
- The proportion of subjects referred to hospital at index consultation (day 0)
- The proportion of subjects referred to hospital during follow-up (day 1 to day 30)
- The proportion of subjects admitted to hospital at index consultation (day 0)
- The proportion of subjects admitted to hospital during follow-up (day 1 to day 30)
- The proportion of subjects who died at index consultation (day 0)
- The proportion of subjects who died during follow-up (day 1 to day 30)
- The proportion of subjects with full clinical recovery at day 7
- The proportion of subjects with full clinical recovery at day 30
- Patient's satisfaction (as part of the nested qualitative study)
- Parent's satisfaction (as part of the nested qualitative study)
- Physician's satisfaction (as part of the nested qualitative study)

- Cost-effectiveness of the intervention: healthcare expenditures in terms of hospitalization, consultations, pharmaceuticals (reimbursed and non-reimbursed), productivity, quality of life
- Adherence to the diagnostic algorithm
- The proportion of subjects who actually took antibiotics (from day 0 to Day 30)

Covariates (predictors in the model)

Important predictors were chosen a priori based on expert opinion by [name] [name].

Predictor	Measurement scale	Df needed
Study arm	Binary: intervention versus control	1
Age	Continuous	1

Handling of missing values and other data conventions

1. REDCap Data

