Drop-outs are unlikely to be a large problem since there will be only one study visit complemented by the collection of follow-up information.

We will analyse the whole population for the primary analysis and perform a sensitivity analysis excluding the low recruiting practices (less than 10 patients recruited for 12 months) to avoid our results to be susceptible to selection bias. In previous trials this resulted in approximately 10% of practices.

Practices that do not recruit children at all will be stopped after the first two monitoring visits and replaced by new practices to avoid reducing the total number of clusters available for analysis.

The percentage of missing data for the primary outcome of antibiotic prescribing proportion is expected to be low as this will be registered at the first contact consultation. In our previous ERNIE2 trial, we found 4% of missing data for the primary outcome of antibiotic prescribing proportion. Multiple imputation will be considered for the primary outcome measure as well as missing values for patient-reported outcomes (if there are any). Other outcomes will be collected from the patient health record of the physician.

Multiple imputation will be applied to deal with missing data. Imputation will be performed for the binary outcome variable and logistic regression will be used as imputation model. Predictors for the imputation model are baseline patient characteristics and intervention.

2. ARON App Data

A substantial drop-out rate in app completion is anticipated, with non-completion of the app not considered grounds for exclusion from the study. To address this, proactive measures were introduced to enhance participation rates, such as the provision of information about the smartphone app and instructions on installation to children and their parents during the baseline consultation. Additionally, the app was made available in three languages (Dutch, French, English).

Multiple imputation will be applied to deal with missing data. For imputation of continuous variables, a linear regression model will be employed, with baseline patient characteristics and intervention serving as predictors for the imputation model.

3. Administrative Data

Multiple imputation, following Rubin's rules, will be utilized to address missing data. Predictors for the imputation model will include baseline patient characteristics and the intervention.

4. Interview Transcripts

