Imputation techniques are not applicable in this dataset.

Statistical Methodology

Statistical Procedures

-

Baseline characteristics & Clinical features

Presentation of baseline characteristics of the study population and comparability of the two arms will be based on the following variables:

- Age (median and 25-75 percentiles)
- Gender (percentage)

Baseline characteristics and clinical features will be reported using frequencies and percentages, means and standard deviations or medians and interquartile ranges, and minimum / maximum, as appropriate.

Primary endpoint

For the analysis of the primary outcome, we will use a mixed-effects logistic regression analysis to account for the clustering at practice level. The child's age and study arm will be included as predefined covariates in the model. We will do this using R software using the 'glmer' function of the 'lme4' package. Results will be reported by an odds ratio (OR) with 95% confidence intervals.

Multiple imputation will be applied to deal with missing data. Ten complete datasets will be constructed and analysed. The 10 results will be combined into a final result following Rubin's rule.

We will analyse the primary endpoint according to the intention-to-treat (ITT) approach, given the pragmatic nature of our trial.

The participating physicians were asked to recruit children with an acute illness consecutively. GPs were likely to have breached the assumption of consecutive inclusions if they:

- recruited fewer than 10 patients per year;
- performed a POC CRP test on nearly all (>90%) of the included children; and/or
- included nearly exclusively children (>90%) based on a negative result on all three items of the clinical decision tree that do not need antibiotics and exclude those that might need antibiotic treatment.

Apart from the intention-to-treat analysis, a per protocol sensitivity analysis will be performed only considering physicians who have recruited children consecutively.

Secondary endpoint – Proportional measures

We will provide a descriptive analysis of the proportion of subjects with the outcome of interest for each randomization group.

A mixed-effects logistic regression model will be employed to address clustering at the practice level. The child's age and study arm will be included as predefined covariates in the model. Odds ratios, along with their corresponding 95% confidence intervals will be reported.

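### Minor: randomisation is stratified by academic centre, but no planned outcome model includes centre and no reason is given; any effect is conservative, and its size is unknown

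*SAP*

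**What the plan says.** Protocol section 8.1 randomises practices 1:1 in blocks of four with a "block randomization system stratified per recruiting academic centre", and the SAP's Randomization section repeats this. The stated purpose is balance between arms within each region. There are six centres and 122 practices.

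The SAP's covariate section says "Important predictors were chosen a priori based on expert opinion", and its table has two rows: study arm and age. For the primary endpoint it says: "The child's age and study arm will be included as predefined covariates in the model". The same sentence serves the secondary and exploratory proportions and the Cox model for time to recovery, each with clustering at practice level only.

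Protocol section 11.3.2 says: "We will use a mixed-effects logistic regression analysis to account for the clustering at practice level". It goes on to allow further unspecified terms, of which only age is named; section 11.3.3 does the same.

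For missing data the SAP says: "Predictors for the imputation model are baseline patient characteristics and intervention". Neither document names centre in any of these models or explains its absence.

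**The concern.** An analysis should normally reflect the restrictions placed on the randomisation. Stratifying by centre puts about equal numbers of practices from each centre in each arm, so differences between centres largely cancel from the arm comparison. A model that knows only about practices cannot see this. It counts between-centre variation as ordinary practice-to-practice variation and carries it into the standard error. If centres differ, the reported interval tends to be wider than the real uncertainty, and the test tends to reject a true null less often than 5%.

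What is at stake is the calibration of the interval and p-value, not the odds ratio.

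**Working it through.** **Inputs from the documents.** Six centres, 122 practices and blocks of four; 20.65% vs 14.35%, cluster size 50, ICC 0.063, two-sided 5%, 90% power; total 7000 children (SAP, Sample size calculation). For secondary outcomes the ICC is 0.025 (Protocol 11.1.1).

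**Assumed, not in the documents.** The share f of between-practice variance that lies between centres (0, 10% or 20%), with the ICC of 0.063 taken to include it; in the simulation, centre sizes of 36/24/20/16/16/10 practices.

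**Step 1: the plan's sample size.** Design effect = 1 + 49 × 0.063 = 4.087. Clusters per arm = (1.960 + 1.282)² × [0.2065 × 0.7935 + 0.1435 × 0.8565] × 4.087 / [50 × 0.063²] = 62.05, rounded up to 63. That gives 126 × 50 = 6300 children, and 6300/0.9 = 7000. The printed figures reproduce from the printed command. The full ICC is used, with no credit for stratification, so leaving centre out of the model takes nothing from the planned power.

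**Step 2: simple formula.** With m = 7000/122 = 57.4 children per practice, the variance of a practice mean is proportional to ICC + (1 − ICC)/m without centre and to (1 − f) × ICC + (1 − ICC)/m with it.

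- Without centre: 0.063 + 0.937/57.4 = 0.0793.
- f = 10%: 0.0567 + 0.0163 = 0.0730; SE ratio √(0.0793/0.0730) = 1.042.
- f = 20%: 0.0504 + 0.0163 = 0.0667; SE ratio 1.090.
- By the same formula, f = 5% gives 1.02 and f = 30% gives 1.15.

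**Step 3: simulation.** Random-intercept logistic model fitted by maximum likelihood, 122 practices, 7000 children, stratified blocks of four, age left out; 20,000 runs per setting with no effect and 10,000 with the planned effect.

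| Assumed centre share f | 0 | 10% | 20% |
|---|---|---|---|
| Formula: SE without / with centre | 1.00 | 1.04 | 1.09 |
| Planned model: SE / true spread, no effect | 0.99 | 1.03 | 1.05 |
| Planned model: SE / true spread, planned effect | 0.99 | 1.01 | 1.04 |
| Type I error, planned z-test | 5.6% | 4.5% | 4.3% |
| Type I error, centre added, plain z-test | 6.1% | 5.8% | 6.1% |
| Type I error, centre added, scaled SE and t on 115 df | 5.2% | 4.9% | 5.2% |

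The spread of the estimated log odds ratio under no effect was the same without and with centre (0.1416 and 0.1417 at f = 0; 0.1309 and 0.1307 at 20%). With the planned effect and f = 10%, the mean estimate was −0.470 in both models.

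**Step 4: why the two methods differ.** Six centres of the assumed sizes realise on average only 1 − (36² + 24² + 20² + 16² + 16² + 10²)/122² = 1 − 2884/14884 = 0.81 of the nominal centre share. The variance without centre is then 0.063 × (1 − 0.19f) + 0.0163, and the ratios fall to about 1.03 and 1.07. Maximum likelihood also runs about 1% low (the 0.99 at f = 0). Together these largely close the gap.

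**Step 5: power.** Planned model vs centre with the corrected test: 91.7 vs 91.1%, 92.1 vs 92.5% and 92.9 vs 94.1% at f = 0, 10% and 20%. When both tests are held at exactly 5%: 90.8 vs 90.7%, 92.7 vs 92.6% and 93.8 vs 93.9%.

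**Step 6: secondary binary outcomes.** Formula only, ICC 0.025: design effect 1 + 56.4 × 0.025 = 2.41. Replacing 0.025 by 0.025 × (1 − f) gives SE ratios of about 1.03 and 1.06. The Cox model was not simulated.

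**The case against.** The strongest reply is that the size is assumed throughout and may be nil. Protocol section 8.4 gives a reason for centres to differ, since "each academic centre will regionally, according to their own customs for recruitment" approach physicians. It also standardises the investigator-meeting information, and section 9 describes a general training session for all participating physicians. A smaller simulation at a 5% share (3000 runs, equal practice sizes) gave an SE-to-spread ratio of 0.997, with a Monte Carlo error of about 1.3%, so the plan is then well calibrated. This stands: the omission is certain, its size is not.

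A second reply is that the ordinary remedy is no better. Centre with a plain Wald test runs at about 6%, an anticonservative error about as large as the conservative one it removes. This also stands, and is why the fix needs a small-sample reference. That correction is a separate matter from centre: with no centre differences the planned z-test is already at 5.6%.

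A third reply, that the protocol's open wording on further terms could cover centre, does not stand. It does not prespecify centre, and the SAP's covariate table lists only arm and age.

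A reader might infer more than the documents support:

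- **Biased effect or excess false positives.** Adding centre leaves the estimate unchanged, and where centres differ the planned test errs towards conservatism.
- **Lost power.** The sample size took no credit for stratification, and at equal test size centre gains nothing.
- **Harder non-inferiority.** The margins in Protocol 11.1.1 are in days and percentage points, whereas the models report odds and hazard ratios. A slightly wider ratio interval changes no stated decision.
- **Time to recovery in general.** The SAP's log-rank test states no allowance for practice clustering. That problem runs in the opposite direction, does not depend on centre, and should be raised separately.

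**Conclusion.** The point holds as a minor, nearly free improvement. Centre restricts the randomisation but is absent from the covariate table, the logistic and Cox mixed models and the imputation models, without explanation. The direction is clear: if centres differ, the standard error tends to be too large.

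The excess is about 0, 1–4% and 4–9% at assumed centre shares of 0, 10% and 20%, the range reflecting the method used. No single figure can be defended from the documents, because they report neither the between-centre variance nor the number of practices per centre. The calculations for the primary outcome also assume a logit-normal practice effect and near-equal practice sizes, and they leave out age.

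**What to change.** Add academic centre (six levels, fixed effect, 5 df) to the SAP covariate table, to the primary, per-protocol and secondary mixed-effects models including Cox, and to the imputation models. Leave it out only where events are too few, such as death. If the sponsor prefers to omit centre altogether, the SAP should say why.

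For the logistic models, use a small-sample reference in place of the plain z-test. One option is to multiply the SE by √(K/(K − 7)) and use t on K − 7 df, where K is the number of practices analysed and 7 counts the intercept, arm and five centre terms. For 122 practices this is √(122/115) = 1.030 and 115 df. If 5% or 10% of practices are excluded (the approximate figures in Protocol 11.3.4 and the SAP), K is 116 or 110 and the df are 109 or 103. This was checked for the primary outcome only. The trial statistician should confirm it, or choose another method, for the secondary, Cox and per-protocol analyses and for the pooled imputations, where the SAP says "The 10 results will be combined into a final result following" Rubin's rule.

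The cost is text edits in the SAP and Protocol 11.3.2–11.3.3 and a few lines of code. Centre is known from randomisation, so no new data are needed. If centres do not differ, nominal power is 0.6 points lower (91.1 vs 91.7%), mostly because the planned test then runs at 5.6%; at equal test size the loss is 0.1 point.

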The S62005 ARON trial was planned before the COVID-19 pandemic. Though, the trial actually started in the initial part of the pandemic, just as the Delta variant (second wave) was first emerging: early 2021. The ARON trial kept going through all subsequent COVID-19 waves and is currently still ongoing.

The COVID-19 pandemic has shown that antibiotic prescribing has (for the better) declined during the pandemic, as shown by several studies and reports:

- https://www.ecdc.europa.eu/en/news-events/reported-decrease-antibiotic-consumption-across-eueea- during-covid-19-pandemic

KCE Trials programme

This has urged us to revise our sample size calculation, based on the overall prevalence found in the first patients recruited, given the start of our trial during the pandemic.

This amendement concerns a clarification of the impact the COVID-19 pandemic has had on recruitment as well as the overall prevalence of our primary outcome, the antibiotic prescribing rate in children.

AIMS

With this amendment, we aim to:

- (1) investigate the influence of the COVID-19 pandemic on antibiotic prescribing rates in practices included in the ARON trial and (2) redetermine the required sample size for the ARON trial.
- (3) monitor whether inclusions were done consecutively, as per the study protocol, in order to minimize selection bias.

METHODS

1. Audit of antibiotic prescribing rate before and during the COVID-19 pandemic

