Contact Datum Is kleiner dan of gelijk aan 31/10/2022 ARON 2.En de periode dat ze gerekruteerd hebben tijdens de trial (gemakkelijk te vinden in Redcap - bv 1 mei 2021 t/m 30 november 2022). b.Hoeveel kinderen hebben minstens 1 AB voorschrift gekregen						
Medicatie	BCFI boom	ls gelijk aan	Antibacteriële middelen			
Contact	Datum	ls kleiner dan of gelijk aan	31/10/2022			
Patiëntenadministratie	Geboortedatum	ls kleiner dan of gelijk aan	30/11/2020			
Contact	Datum	ls groter dan of gelijk aan	01/05/2021			
Medicatie	Datum	ls groter dan of gelijk aan	01/05/2021			
Patiëntenadministratie	Geboortedatum	ls groter dan of gelijk aan	01/05/2009			
Contact	Auteur	ls gelijk aan				
Contact	Туре	ls gelijk aan	Consultatie			
Medicatie	Datum	ls kleiner dan of gelijk aan	31/10/2022			

Figure 8. Audit questions (after start of the trial) in CareConnect software (Corilus).

Most software packages, e.g., CareConnect², Daktari³, HealthOne⁴, of which the former dominate the market, have a statistics/search module. This allows for easy and uniform access to the required data.

2. Sample size calculation

The original sample size calculation was based on previous data, assuming an overall prescribing rate of 26.5% in those children recruited for our trial.

The overall prevalence was found to be 18% overall in children recruited in the first 4938 patients recruited in the ARON trial.

If we were to assume a reduction of 5.3% (proportionate to our original reduction) between the usual care group and the intervention group, using a 5% significance level (alpha 0.05), an intracluster correlation coefficient (ICC) of 0.063 (based on data from the ERNIE2 study in the exact same population), and power of 90% (beta 0.1), this would require **63 clusters of 50 patients** in both arms, resulting in **6300 children**.

R code:

We used the n4props-function in the R package CRTSize, using the following command:

n4props(0.2065,0.1435,50,0.063, alpha = 0.05, power=0.9, AR=1, two.tailed=TRUE, digits=3)

Considering the pragmatic nature of this trial and in correspondence with the 10% of practices performing nonconsecutive inclusion of patients (high risk of selection bias) during the ERNIE2 trial, we will perform sensitivity analyses only considering physicians who have recruited in a consecutive way. Taking into account the required sample size for this analysis of the primary study outcome, these assumptions result in a total sample size of 7000 patients for the primary study outcome.

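### The primary model adjusts only for arm and age, leaving out the practice's audited pre-trial prescribing rate (a likely gain in precision) and calendar time (a cheap robustness check)

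*SAP*

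**What the plan says.** The SAP (Endpoints and covariates) lists two predictors with one degree of freedom each: arm, and age as a continuous variable. Under Statistical Methodology, Primary endpoint, the model is a mixed-effects logistic regression with clustering at practice level, and "The child's age and study arm will be included as predefined covariates in the model". The planned sensitivity analysis restricts the set of physicians; it does not change the covariates.

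Protocol section 11.1.2 treats calendar time as relevant to the primary outcome. It says that "The ARON trial kept going through all subsequent COVID-19 waves and is currently still ongoing". One of its aims is to "investigate the influence of the COVID-19 pandemic on antibiotic prescribing rates in practices included in the ARON trial", by means of an audit that extracts, practice by practice, the proportion of children with at least one antibiotic prescription before and during the pandemic. The audit is used to describe the COVID-19 effect and to help check consecutive recruitment. It is not among the four data sources in the SAP, and no model uses it.

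Practices do not all start together. Protocol section 8.4 describes two stages, "with stage 1 acting as a run-in period before all practices will be asked to start recruiting patients", and the SAP adds: "Practices that do not recruit children at all will be stopped after the first two monitoring visits and replaced by new practices".

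**The concern.** In a cluster trial with a sizeable ICC, the error in the treatment effect comes mainly from practices that differ in their habits. A child-level covariate such as age removes little of that. A practice-level measure of the same behaviour, taken before the trial, is the natural covariate for it, and the protocol already plans to collect one.

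The index date must also be known, since the follow-up form falls due 30 days after the index consultation. Yet the SAP neither adjusts for it nor plans a table of it by arm. If enrolment timing did drift apart between arms, the planned outputs would not show it. If either term were added after the results by arm were known, it would look chosen to fit them.

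**Working it through.** **Inputs from the documents.** R command in the SAP and protocol 11.1.2: control 0.2065, intervention 0.1435, m = 50 per practice, ICC = 0.063, two-sided alpha 0.05, power 0.90. Text: a reduction of 5.3 points, 63 practices per arm, 6300 children, raised to 7000; 122 practices in all. **Assumed:** r, the practice-level correlation between the audited rate and prescribing in the trial, at 0.3, 0.5 and 0.7.

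**1. Reproduce the plan.** Children per arm before clustering:

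n = (1.96 + 1.2816)² × [0.2065 × 0.7935 + 0.1435 × 0.8565] / 0.063² = 759.2

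Design effect (DE) = 1 + 49 × 0.063 = 4.087. Practices per arm = 759.2 × 4.087 / 50 = 62.05, rounded up to 63. That gives 6300 children, and 6300 / 0.9 = 7000. The plan's figures reproduce.

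**2. Two starting points for power.** The command codes a difference of 0.2065 − 0.1435 = 6.3 points; the text says 5.3. With 0.2065 and 0.1535 (difference 5.3 points, mean 18%), power at 63 × 50 per arm is 77.5%, against 90.4% for the coded values. Using 61 practices per arm with 7000/122 = 57.4 children each barely changes this (77.4% and 90.4%). Both starting points are carried forward.

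**3. Where the error comes from.** Of the DE of 4.087, the clustering term is 49 × 0.063 = 3.087, so 3.087 / 4.087 = 76% of the variance is due to differences between practices.

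**4. Gain from the audited rate.** Adjusted ICC = 0.063 × (1 − r²); DE = 1 + 49 × adjusted ICC; SE² = [p1(1−p1) + p2(1−p2)] × DE / (63 × 50); power = Φ(difference/SE − 1.96).

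| r (assumed) | Adjusted ICC | DE | Variance cut | Power, 6.3 points | Power, 5.3 points |
|---|---|---|---|---|---|
| 0 | 0.0630 | 4.09 | – | 90.4% | 77.5% |
| 0.3 | 0.0573 | 3.81 | 7% | 92.3% | 80.3% |
| 0.5 | 0.0473 | 3.31 | 19% | 95.2% | 85.4% |
| 0.7 | 0.0321 | 2.57 | 37% | 98.4% | 92.8% |

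These figures are on the scale of a difference in proportions, as in the plan's own calculation. The SAP's model is logistic, so they are approximate.

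**5. Precision gain from calendar time.** Take an extreme case: the whole gap between the planning rate of 26.5% and the observed 18% (8.5 points) occurs inside the trial, split half and half. Period then explains 0.25 × 0.085² / (0.18 × 0.82) = 1.2% of child-level variance, which is negligible.

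**6. Bias from calendar time.** A simulation used 61 practices per arm, 57 children each, ICC 0.063 and the same extreme 8.5-point swing, with practice means compared and no period adjustment. When both arms had the same enrolment timing, bias was about 0.0 points and type I error about 0.05. Bias appeared only when timing was made to differ by arm: a 10-point difference in period share gave about 0.8 points of bias and type I error 0.07; a 20-point difference gave about 1.6 points and 0.13. The swing and both timing differences are assumptions. Chance alone gave an SD of the difference in period share of 0.055 to 0.073.

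**The case against.** The strongest reply is that leaving out an optional prognostic covariate does not invalidate a randomised comparison. The covariates were fixed in advance on expert opinion, and the gain depends on a correlation that nobody has reported. All of that stands: this is a lost opportunity, not an error that biases the result.

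The second reply is that the audit is an imperfect baseline, and this also stands. It counts children with at least one prescription over a window, not prescribing per acute consultation. The example queries use calendar 2018 for the denominator but May 2017 to November 2018 for the numerator. The pre-pandemic window is matched to each practice's own recruiting period, which falls after randomisation, so windows could differ in length between practices. Only most software packages are said to have a search module, so coverage of all practices is not assured. These weaknesses push r towards the low end and are why the fix carries conditions.

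A reader might go further and infer that prescribing fell by about a third during recruitment, so that the arms are confounded by calendar time. The documents do not support this. The planning figure came from previous trial data, "assuming an overall antibiotic prescribing proportion of 26.5% in those children recruited for our trial", and the comparison figure is pooled over arms and over time: "The overall antibiotic proportion was found to be 18% in the first 4938 patients recruited in the ARON trial". The relative gap of 32% is between past data and this trial, which began in early 2021 with the pandemic already under way. Practices were randomised 1:1 to concurrent arms in blocks of four within academic centre, so a secular trend alone affects both arms alike, and the confidence interval covers chance imbalance. Different timing by arm is possible, because physicians are unmasked, entry is staged and no allocation rule is stated for replacement practices. No passage shows that it happened.

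**Conclusion.** The point holds as a matter of precision and robustness. The primary model omits a practice-level baseline that the protocol already plans to collect, in a design where about 76% of the error variance lies between practices. The likely gain is a variance cut of 7% to 37% for an assumed r of 0.3 to 0.7. That is worth roughly 2 to 8 points of power at the coded effect and 3 to 15 points at the effect in the text. The size rests wholly on r, on equal practice sizes and on the planned ICC. The starting power depends on whether 5.3 or 6.3 points is meant, which the sponsor should settle separately. For calendar time the case is weaker: negligible precision, and bias only if enrolment timing differed by arm. That justifies a pre-specified check and a table of dates, not a statement that the primary comparison is confounded.

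**What to change.** Amend the SAP before any outcome is analysed by arm:

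1. Add the practice's audited pre-trial prescribing rate to the covariate table and the primary model. Take numerator and denominator from one common, fixed pre-trial window for all practices, and list the audit as a data source. First check completeness without using outcome data, against a coverage threshold written down beforehand. If coverage falls short, use the rate in a sensitivity analysis only. State how practices without a value are handled.
2. Add season or calendar quarter of the index consultation, at minimum as a pre-specified sensitivity analysis, and tabulate index dates by arm.
3. Keep the arm-and-age model as a sensitivity analysis.

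The cost is SAP wording, one practice-level term across 122 practices, and a few degrees of freedom for period among about 7000 children. Audit queries may have to be rerun on the common window, and some practices may lack a value.
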